6.2 SUMMARIES OF CONDUCT OF STUDY

The number of patients who are randomized, who are RT-PCR positive, *who are treated*, and who discontinue or complete the study will be summarized by treatment group. Reasons for premature study withdrawal will be summarized.

Eligibility criteria deviations and other major protocol deviations will be listed and summarized by treatment group.

6.3 SUMMARIES OF DEMOGRAPHIC AND BASELINE CHARACTERISTICS

Demographic and baseline characteristics (including age, sex, race, region, NEWS2, RT-PCR status, time from symptom onset to study treatment) will be summarized using means, standard deviations, medians, and ranges for continuous variables and proportions for categorical variables, as appropriate. Summaries will be presented by treatment group. These will be summarized for the modified-ITTI and safety populations.

6.4 EFFICACY ANALYSES

Efficacy analyses will *use the mITTI population, which includes all patients randomized who received at least one dose of study drug with patients grouped according to the*

treatment assigned at randomization and are centrally assessed RT-PCR positive for influenza *at any timepoint*.

In addition to the analyses described in Section 6.4.1 and Section 6.4.2, the following analyses will be performed for the primary efficacy endpoint and the key secondary efficacy endpoints, *as appropriate*. Details of these analyses will be described in the SAP:

- Sensitivity analyses to evaluate the robustness of results to the primary analysis methods (e.g., handling of dropouts)
- *Descriptive subgroup* analyses to evaluate the consistency of results across prespecified subgroups (e.g., based on age, sex, race/ethnicity, stratification factors, and patients taking anti-influenza drugs prior to enrollment)

Hypothesis tests will be two-sided at the 5% significance level, unless stated otherwise.

To manage the overall type I error, the endpoints will be tested sequentially. The order of testing will be as follows:

- TTCI
- Response rates of the 6-point ordinal scale at Day 7
- *Time to Clinical Response*

If the primary efficacy analysis hypothesis test result is not statistically significant (*i.e.* $p > 0.05$), the hypothesis below that result in the hierarchical chain will be considered exploratory and no claims of statistical significance will be made. *The same rules apply to the next endpoint in the chain.*

6.4.1 Primary Efficacy Endpoint

The primary efficacy objective for this study is to evaluate the efficacy of baloxavir marboxil plus a SOC NAI, compared with matching placebo plus SOC NAI on the basis of the following endpoint:

- TTCI (defined as time to hospital discharge or time to NEWS2 of ≤ 2 and maintained for 24 hours, whichever comes first)

The median TTCI will be compared between the baloxavir marboxil plus SOC NAI and matching placebo plus SOC NAI arms using the stratified log-rank test within three regions (*i.e.*, North America, EMEA, ROW), NEWS2 (≤ 7 , > 7), and time from symptom onset to study treatment (≤ 48 hours, > 48 hours) included as the stratification factors. The Kaplan-Meier plot, median time to response, 95% CIs, and p-values will be presented.

The log-rank test requires the assumption of proportional hazards to be met. The proportional hazards assumption will be tested graphically using the log cumulative hazard plot by treatment group. The plots for each treatment group will be parallel if the

proportional hazard assumption holds. *Using a Cox model, the slope of a linear regression will also be tested and a plot of scaled Schoenfeld residuals against the Kaplan-Meier estimator investigated.*

Should the proportional hazards assumption be violated, the Gehan-Wilcoxon test will be used to analyze the data *as the logrank test can be under powered in this situation.* All investigations will be detailed in the statistical section of the CSR.

The estimand is the median change in TTCI. This absolute measure will be assessed over the duration of the study (35 days). Intercurrent events are those that occur after treatment initiation and either preclude observation of the variable or affect its interpretation. Intercurrent events will be accounted for through censoring rules. Patients who are lost to follow-up, who do not have a clinical response event, who die or discontinue for any reason prior to achieving a clinical response event will be censored at their last contact date or date of death, whichever is applicable. No dose reductions or treatment cross-overs are anticipated.

As specified in Section 6.4, the primary efficacy analysis population will be the modified-ITTI population, which consists of all patients who were randomized to treatment, received a dose of study drug, and were RT-PCR positive for influenza *at any timepoint.*

A sensitivity analysis will be conducted where patients who are lost to follow-up or who do not have a clinical response event will be assumed to have had an event at 28 days. A sensitivity analysis for *patients* who discontinue for any reason prior to achieving a clinical response event will be performed to investigate potential confounding factors. *A sensitivity analysis, considering death as a competitive event, using a competing risk model will be conducted if there are a sufficient number of deaths or an imbalance between groups in deaths and reason attributed. These and any further sensitivity analyses will be fully detailed in the SAP.*

Missing data handling rules for the components of the NEWS2 score will be specified in the SAP.

6.4.2 Key Secondary Endpoints

6.4.2.1 *6-Point Ordinal Scale Measured at Day 7*

For the key secondary endpoint of 6-point ordinal scale the response rate of the scale will be measured at Day 7. The 6-point ordinal scale will be analyzed using the Cochran-Mantel-Haenszel test statistic stratified by region (i.e., North America, EMEA, ROW), NEWS2 (≤ 7 , > 7), and time from symptom onset to study treatment (≤ 48 hours, > 48 hours).

For the ordinal endpoint, missing data will be imputed by using the patient's last non-missing score for any patient with a missing response at Day 7. If the patient died

prior to Day 7, the patient will be included in the death category. The proportion of patients with a response in each category will be summarized by treatment group and Cochran-Mantel-Haenszel test statistic result presented.

A sensitivity analysis will be conducted where missing scores at Day 7 will be replaced by the patient's last non-missing score +1 (*i.e.*, *one ordinal category worse*). If the patient died prior to or on Day 7, the patient will be included in the death category.

6.4.2.2 *Time to Clinical Response*

The additional key secondary endpoint of the "time to clinical response" will be based upon hospital discharge, fever, and oxygen saturation, and two or more of the following: improved respiratory status, heart rate, or systolic blood pressure. The exact criteria for each parameter are as follows:

Temperature:^a

- $\leq 36.6^{\circ}\text{C}$ ($\leq 97.9^{\circ}\text{F}$)—axillary, or
- $\leq 37.2^{\circ}\text{C}$ ($\leq 99^{\circ}\text{F}$)—oral, or
- $\leq 37.7^{\circ}\text{C}$ ($\leq 99.9^{\circ}\text{F}$)—rectal, core, or tympanic

AND

Oxygen Saturation:^{b,c}

- $\geq 95\%$ (without supplemental oxygen)

AND two of the following three:

Respiratory Status:

- Return to pre-morbid oxygen requirement (patients with chronic oxygen use), OR
- Need for supplemental oxygen (given in any way—ventilator, non-invasive ventilation, facemask, face-tent, or nasal cannula) to no need for supplemental oxygen, OR
- Respiratory rate ≤ 24 per min (without supplemental oxygen)

Heart Rate:

- ≤ 100 beats per min

Systolic blood pressure:^d

- ≥ 90 mmHg
- OR

Hospital Discharge

- a Without the use of antipyretics within 8 hours.
- b A patient with a history of chronic hypoxia (without supplemental oxygen) will satisfy the normalization criteria for oxygen saturation if the value (without supplemental oxygen) is $\leq 2\%$ from the patient's historical oxygen saturation before enrollment as documented in the patient's medical records, if available
- c This requirement is waived for patients with a history of chronic supplemental oxygen requirement who have an oxygen saturation $< 95\%$ with supplemental oxygen documented in the patients' medical records within 12 months of enrollment.
- d Without inotropic support given within 2 hours of assessment.

For patients who achieve four of the five vital sign resolution criteria above, both the temperature and oxygen saturation response criteria must be maintained for 24 hours for the clinical response endpoint to be met.

Time to clinical response will be analyzed using *similar* methods and sensitivity analyses as specified for the primary endpoint. Patients who are lost to follow-up, who do not have a clinical response, or who die will be censored at their last contact date or date of death, whichever is applicable. *Further details on methods and missing data rules will be fully detailed in the SAP.*

6.4.3 Secondary Efficacy Endpoints

The *other* secondary endpoints for this study are as follows:

- The incidence of mechanical ventilation
- Duration of mechanical ventilation
- Incidence of ICU stay
- Duration of ICU stays
- Time to clinical failure (defined as the time to death, mechanical ventilation, or ICU admission, corresponding to ordinal scale categories 6, 5, and 4, respectively, from baseline)
- Time to hospital discharge
- Incidence of influenza-related complications (pneumonia, myositis or rhabdomyolysis, encephalitis or encephalopathy, myocarditis and/or pericarditis, otitis media, sinusitis, exacerbation of COPD/asthma, sepsis, acute lung injury, or acute respiratory distress syndrome)*
- Mortality rate at Day 7
- Mortality rate at Day 28
- Time to NEWS2 of ≤ 2 maintained for 24 hours

* Specific complication eCRF pages with diagnostic criteria for the complications of pneumonia, myositis or rhabdomyolysis, encephalitis or encephalopathy, myocarditis and/or pericarditis, otitis media, sinusitis, exacerbation of COPD/asthma, sepsis, acute lung injury, or acute respiratory distress syndrome will be utilized for these events reported as adverse events after the initiation of study treatment. This data will be subject to a blinded manual medical review of events together with other related eCRF data (e.g., serious adverse event forms as applicable and medical history).

Secondary efficacy *incidence* and rate endpoints will be analyzed using the Cochran-Mantel-Haenszel test statistic stratified by region (North America, EMEA, ROW), NEWS2 (≤ 7 , > 7) and time from symptom onset to study treatment (≤ 48 hours, > 48 hours).

Time to event secondary efficacy endpoints will be analyzed using *similar* methods as specified for the primary endpoint. Patients who are lost to follow-up, who do not have a response, or who die will be censored at their last contact date or date of death, whichever is applicable.

Mortality rates and duration of ICU stays and ventilation will be analyzed descriptively.

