TCID ₅₀	50% tissue culture infectious dose
TQT	Thorough QT
TTAS	time to alleviation of symptoms
TTCI	time to clinical improvement
ULN	upper limit of normal
Vc/F	apparent volume of distribution for the central compartment

1. **BACKGROUND**

1.1 **BACKGROUND ON INFLUENZA**

Influenza is an acute respiratory infectious disease caused by a virus of the orthomyxovirus family. Two forms are known to infect humans, influenza A and B. These viruses cause an acute febrile infection of the respiratory tract after an incubation period of 1 to 4 days, characterized by the sudden onset of fever, cough, fatigue, headache, and myalgia. Annual influenza epidemics are thought to result in between 3 and 5 million cases of severe illness, and between 250,000 and 500,000 deaths every year around the world (WHO 2017).

Although the condition is usually self-limiting in healthy adults, it can be associated with substantial morbidity and occasional mortality in children, the elderly, and the immunocompromised (Paules and Subbarao 2017). Hospitalization due to severe influenza is associated with high mortality (4%–8%), intensive care unit (ICU) admission (5%–17%), and prolonged hospital stays of between 5 and 9 days. During a pandemic season, the outcomes may be more serious, with up to 34% of patients requiring ICU care and a mortality rate as high as 15% (Lee and Ison 2012).

The influenza viruses have a segmented, negative-sense, single-stranded, lipid-encapsulated RNA genome; they range between 80 and 100 nm in size. Subtypes are defined according to glycoproteins present in the viral lipid coat. The hemagglutinin complex (HA) is the major surface protein of the virus. The neuraminidase (NA) proteins are the second major surface proteins in the virion and play a role in enhancing virus penetration of the mucus layer around the target cell and in release of virus from the cell surface. The matrix-2 (M2) protein triggers the disintegration of the virion during virus entry into the cell and may also be involved in protecting the HA prior to assembly of new virus particles.

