4.5.1.1 Sensitivity Analysis

The following sensitivity analyses will be conducted:

1. to examine the effect of subjects who discontinue for any reason prior to achieving a clinical response event
 - patients who are lost to follow-up or who do not have a clinical response event will be censored at 35 days.
 - any imbalance in demographics, disease characteristics and influenza history between treatment arms will be assessed in relation to reasons for discontinuation to identify any confounding factors. Identified confounding factors will be adjusted for in a sensitivity analysis.
 - considering death as a competitive event, using a competing risk model will be conducted if there are a sufficient number of deaths (~10%) or an imbalance between groups in deaths and reason attributed.
2. to examine the effect of artificial support, defined as receiving non-invasive mechanical ventilation, mechanical ventilation, Extracorporeal membrane oxygenation (ECMO) and/or inotropic support
 - patients who met the NEWS2 criteria (≤ 2 for 24 hours) and received artificial support during this time period will be censored at the vital signs assessment where $\text{NEWS2} \leq 2$ at start of 24 hour period.

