Event	Imputation Rule
Patient Discontinued or Lost to follow-up	duration of last incidence uses date of discontinuation or date lost to follow up as the end date
Patient died	duration of last incidence uses date of death as the end date

The analysis of duration of mechanical ventilation will be repeated to include patients whose mechanical ventilation had started before being randomized into the study, who continued to be on mechanical ventilation after receiving first treatment. The duration will be calculated as specified above, except it will start from the start date of mechanical ventilation.

Incidence of ICU stay

Incidence of ICU will be assessed from the ICU admissions log. It will be assumed that, unless a discharge date is available, the first ICU admission is continuous and as such will be counted as one event. This will also be the case for each subsequent event. The number of incidences of ICU stay as well as number and percentage of patients with ICU stay, between start of treatment and end of study will be presented.

This analysis will be repeated to include patients who were admitted to ICU prior to randomization in the study, but remained in ICU after first treatment. The number of incidences of ICU stay, and the number and percentage of patients with ICU stay whilst on treatment will be presented.

Duration of ICU stays

Duration of ICU stay will be calculated in hours as the sum of the duration of ICU stay, based on the admission and discharge date and time of the ICU admissions log: (ICU discharge datetime – ICU admission datetime).

Patients who are in ICU until end of study will be censored at last available date and time. Patients who die will be censored at their date of death.

Partial admission and discharge dates and times will be imputed based on available data, following a conservative approach.

This analysis will be repeated to also include patients who were admitted to ICU prior to randomization in the study, but remained in ICU after first treatment.

Time to clinical failure

Time to clinical failure, in hours, is defined as the time from start of treatment to death, mechanical ventilation, or ICU admission, corresponding to ordinal scale categories 6, 5, and 4, respectively.

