Table 11 Time to NEWS2 of ≤ 2 maintained for 24 hours and Censoring

Event	Censor	Date and Time
NEWS2 ≤ 2 for 24 hours	No	vital signs assessment where NEWS2 ≤ 2 at start of 24 hour period
NEWS2 ≤ 2 prior to discharge	No	first vital signs assessment where NEWS2 ≤ 2 prior to discharge
Death prior to achieving NEWS2 ≤ 2 for 24 hours	Yes	last vital signs assessment prior to death
Discontinuation for any reason prior to achieving NEWS2 ≤ 2 for 24 hours	Yes	last vital signs assessment prior to discontinuation
Lost to follow-up	Yes	last vital signs assessment
No NEWS2 ≤ 2 for 24 hours	Yes	last vital signs assessment

Incidence and rate endpoints will be analyzed using the Cochran Mantel-Haenszel test statistic stratified by region (North America, EMEA, ROW), NEWS2 at baseline (≤ 7 , >7) and time from symptom onset to study treatment (≤ 48 hours, > 48 hours).

Time to event secondary efficacy endpoints will be analyzed using the same method and sensitivity analyses (where required) as specified for the primary endpoint (see Section 4.5.1).

Mortality rates and duration of ICU stays and ventilation will be analyzed descriptively.

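### Time to clinical failure borrows the primary endpoint's median, which is not expected to be reached in a seasonal population, so no effect estimate is planned; the protocol and SAP also disagree on whether death is censored

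*Protocol*

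**What the plan says.** Protocol 6.4.3 lists the endpoint as "Time to clinical failure (defined as the time to death, mechanical ventilation, or ICU admission", tied to ordinal categories 6, 5 and 4. It then sends all secondary time-to-event endpoints to methods similar to the primary's and adds one censoring sentence for all of them: "Patients who are lost to follow-up, who do not have a response, or who die will be censored at their last contact date"; for those who die, the cut-off may instead be the day they died. No exception is made for clinical failure.

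SAP 4.5.3 defines the endpoint as "the time from start of treatment to death, mechanical ventilation, or ICU admission". Its Table 9 marks death as not censored, including a death reported after discontinuation, and censors patients lost to follow-up at the last available date. For the analysis it says: "Time to event secondary efficacy endpoints will be analyzed using the same method and sensitivity analyses (where required) as specified for the primary endpoint".

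The inherited method is in Protocol 6.4.1, "The Kaplan-Meier plot, median time to response, 95% CIs, and p-values will be presented", and in SAP 4.5.1, which adds the difference in medians. The first inherited sensitivity rule, in SAP 4.5.1.1, is that "patients who are lost to follow-up or who do not have a clinical response event will be censored at 35 days". The same section has a competing-risk model for death, to be run if deaths reach roughly 10% or are imbalanced between arms. SAP Table 15 allows no imputation for time to clinical failure. SAP 3.3, which lists changes from Protocol version 2, mentions the interim statistic and the clinical response definition only.

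**The concern.** Rules that suit an event nearly everyone reaches within days do not suit an adverse event that most patients avoid.

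- **Summary.** If fewer than half of an arm fail, the Kaplan-Meier curve stays above 50% and the median, its interval and the difference in medians cannot be estimated. Nothing else is planned as an effect measure.
- **Death.** A sentence that censors deaths makes sense for time to discharge. Applied to an endpoint that contains death, it contradicts the definition in the same section.
- **Sensitivity analyses.** Censoring a lost patient at Day 35 is unfavourable when the event is improvement. When the event is failure it assumes that the patient stayed failure-free. A model with death as a competing event has no meaning when death is one of the events.

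At stake is whether the trial can say how large any difference in deterioration or death is, with an interval, and whether two readers of the plan would build the same dataset.

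**Working it through.** **Inputs.** The documents give no event count, power or effect size for this endpoint, so there is no stated figure to reproduce beyond the denominator: 366 × 0.75 × 0.96 = 263.5, matching the 264 (176 and 88) in Protocol 6.1. Event rates come from Protocol 1.1: seasonal ICU admission 5–17% and mortality 4–8%; pandemic ICU care up to 34% and mortality up to 15%. How far ICU care and death overlap is not stated, so both extremes are shown.

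**1. Proportion failing.** Full overlap gives max(ICU, death); no overlap gives ICU + death.

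- Seasonal, low figures: 5% to 5 + 4 = 9%, or 13 to 24 events in 264.
- Seasonal, high figures: 17% to 17 + 8 = 25%, or 45 to 66 events.
- Pandemic maxima: 34% to 34 + 15 = 49%, or 90 to 129 events.

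**2. Chance that at least half of an arm fails** (exact binomial, P(X ≥ n/2), ignoring censoring).

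| True proportion | 88 patients | 176 patients |
|---|---|---|
| 25% | 4.0 × 10⁻⁷ | 9 × 10⁻¹³ |
| 34% | 0.0014 | 8.9 × 10⁻⁶ |
| 49% | 0.47 | 0.42 |

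On seasonal figures the curve stays near or above 75% event-free and the median is not reached. At the no-overlap pandemic maximum it could be.

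**3. What the p-value alone can show.** Take a hazard ratio of 63/94 = 0.67 for illustration; this is the ratio implied by the primary sizing (94 against 63 hours, exponential). With 2:1 allocation, power = Φ(√(d × 2/9) × |ln 0.67| − 1.96).

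- d = 13: about 10%.
- d = 66: √14.67 × 0.400 − 1.96 = −0.43, or about 33%.

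A non-significant p-value is therefore the likely result even for a sizeable effect, and without an estimate and interval it says little.

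**4. Death handling, side by side.** Protocol definition: death is a failure. Protocol censoring sentence: patients who die are censored. SAP definition and Table 9: death is an event. SAP 3.3: no entry.

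- Under the SAP, failures lost = 0.
- Under the protocol sentence read literally, the loss is 0 if every death follows ICU care or ventilation. With no overlap it is up to 4/9 = 44% (low seasonal figures) or 8/25 = 32% (high).

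**5. Day-35 rule.** Assume the 4% dropout figure applies within the 264: 264 × 0.04 ≈ 11 patients. Suppose they are lost at the start.

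- Treated as failure-free: 25% becomes 0.25 × 0.96 = 24%; 5% becomes 4.8%.
- Treated as failures: 24 + 4 = 28%; 4.8 + 4 = 8.8%.

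**The case against.** The strongest reply is that the SAP is the operative document and already separates this endpoint from the improvement endpoints. A reader might infer from Protocol 6.4.3 that the trial will drop deaths from its failure endpoint. The documents do not support that: the SAP definition and Table 9 count every death, the sentence introducing Table 9 leaves death out of the censoring reasons, and the protocol defers detailed methods to the SAP. What stands is an unrecorded contradiction.

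A reader might also infer that the median can never be reached. That is too strong. The 25% is not a hard ceiling: it uses seasonal rates only, no separate ventilation rate is given, and SAP 4.5.3 counts non-invasive ventilation in its ventilation incidence, which would raise the proportion if carried over here. Trial patients may also be sicker than the background population. Against this, patients already in ICU or ventilated at the start of treatment fail only by worsening, which lowers it.

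A third inference, that the sensitivity analyses will materially favour a finding of no failure, also fails. They are inherited only where required, Table 9 already censors lost patients at the last available date, Table 15 allows no imputation, and the shift is about 1 percentage point. But nothing says when they are required, or that they are not required here.

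Finally, harm is reported elsewhere: ventilation and ICU incidence, mortality at Days 7 and 28, and the ordinal scale. The endpoint also lies outside the testing hierarchy. That limits the priority of the point, but none of those summaries gives an effect estimate for the composite over time.

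**Conclusion.** The point holds for the summary measure. On the protocol's seasonal rates 5–25% of patients fail, neither arm is expected to reach a median, and the plan names no hazard ratio or fixed-day proportion, so the endpoint would yield a p-value and a plot without an effect estimate. This rests on the Protocol 1.1 rates applying to the trial population and on light censoring; at the pandemic maxima (34–49%) a median could be reached.

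On death, the protocol contradicts its own definition and the SAP, and SAP 3.3 is silent. No deaths are lost if Table 9 is followed. On sensitivity analyses, the two inherited rules are ill-suited but their use is discretionary, and at 4% loss the Day-35 rule matters little. The primary and key secondary conclusions are not affected.

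**What to change.** 1. In SAP 4.5.3, report for time to clinical failure a Cox hazard ratio with 95% CI, stratified by the randomisation factors, and the Kaplan-Meier failure proportion per arm at Day 7 and Day 28 with the difference and its 95% CI. These can replace the median or stand beside it.
2. Restrict the death-censoring part of the Protocol 6.4.3 sentence to time to hospital discharge and time to NEWS2 ≤ 2, or list Table 9's handling of death in SAP 3.3 as a change from the protocol.
3. State in SAP 4.5.3 that the Day-35 censoring rule and the competing-risk model for death do not apply to this endpoint.

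An added analysis that counts loss while still in hospital as failure is optional. The cost is a few sentences, one model and one table. No new data are needed.
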